9.5. Electrocardiogram

Triplicate 12-lead electrocardiograms (ECGs) will be obtained at the Screening visit using an ECG machine that automatically calculates the heart rate and measures PR, QRS, QT, and correct QT intervals. Besides screening, ECG is only required when any suspected cardiac abnormality arise.

Listings of ECG interpretations and ECG values will be provided and worst screening interpretation will be summarized and listed.

9.6. Other Safety Data

9.6.1. Liver Events

A summary of Liver Monitoring/Stopping Event Reporting will be produced. This summary will display:

- Number of subjects with liver monitoring and/or stopping event
- Number of subjects with liver stopping event:
 - Number of subject with start of liver stopping event will be split based on the exposed period.
 - Number of subjects with liver stopping events resolved / not resolved
- Number of subjects with liver monitoring event that never reached stopping criteria:
 - Number of subject with start of liver stopping event will be split by based on the exposed period.
 - Number of subjects with liver stopping events resolved / not resolved
 - Number of subjects with Restart/Re-challenge of events

All liver events information will be presented in separate listings:

- Listing of subjects experiencing liver monitoring/stopping event during the study
- Liver PK
- Liver Biopsy

- Liver Monitoring/Stopping Event Reporting
- Liver Imaging
- Liver Events
- Medical Conditions at Onset of Liver Event
- Other Liver Disease Conditions
- Other Medical Conditions

For each listing all data collected in the eCRF will be listed in detail.

An additional summary of subjects meeting emergent hepatobiliary laboratory abnormality criteria (as defined in protocol section 5.4.3.) will be displayed.

9.6.2. Injection Site Reaction

An injection site reaction is any unfavorable or unintended sign that occurs at the study drug injection site. All subjects must be carefully observed for symptoms of an injection site reaction. Prior to and including through Week 4, subjects will be observed for at least 30 minutes after the SC injection of study drug for symptoms of an injection site reaction.

After Week 4, subjects do not need to be observed for 30 minutes for the post-administration injection-site evaluation if they are self-administering at home. However, subjects should promptly notify the site if they experience a reaction at the site of injection. If an injection site reaction is observed, the subject should be treated at the investigator's discretion.

An injection site reaction will also be reported as an AE in the study.

All data related to injection site reaction will be listed in detail.

9.6.3. Columbia-Suicide Severity Rating Scale

Suicidality assessments are completed at every visit (i.e. at Week 0, Week 2, Week 4, Week 8, Week 12, Week 16, Week 20, Week 24, Week 28, Week 32, Week 36, Week 40, Week 44, Week 48 and Week 52). Assessments are done using the C-SSRS. If a "yes" response is given to any suicidal behavior (not including self-injurious behavior) or a "yes" response to suicidal ideation questions 3, 4 or 5 on the C-SSRS, the investigator will be prompted to discuss the alert with the subject. A standard PSRAE (Possible suicidality-related AE) data collection form is available that is intended to collect detailed information on the circumstances of reported AEs which, in the investigator's opinion, are possibly suicidality-related. A summary table of C-SSRS post-baseline results will be provided. All C-SSRS and Possible Suicidality Related Questionnaire information will be listed in detail.

10. IDMC Reviews

An Independent Data Monitoring Committee (IDMC) will monitor data from this study. The overall responsibility of the IDMC is to protect the ethical and safety interests of subjects recruited into 201677 while protecting as far as possible the scientific validity of the data.

The IDMC will make recommendations concerning conduct of the study, including changes to the informed consent. The IDMC will meet at predefined times to identify potential treatment harm and all-cause mortality/morbidity.

After the initial organizational meeting, the first data review meeting will be held once 12 subjects have completed 12 weeks of treatment. Thereafter, the frequency of scheduled meetings depends on subject enrollment, information accumulated and safety event rates but will occur no less than quarterly.

Full details are provided in the IDMC charter document (dated 20JAN2016).

Due to study termination, the IDMC agreed to have the last formal meeting on Oct 25, 2017. Monthly cumulative SAE listing are sent to the IDMC until study end (LSLV). If the committee has any inquiries regarding safety, they can raise it with PPD and GSK even though no additional formal IDMC meeting is scheduled.

11. Part B

Only demographic and baseline characteristic as well as Safety will be displayed for Part B. All demographic and baseline characteristic as well as Safety summaries produced for Part A will be produced for Part B. Part B outputs will be displayed using the same general layout of Part A outputs, using the same Part A group as the treatment groups.

Each output will be split using a by-line which will contain information on Part B:

- “Never Received OL Sirukumab during Part B” will include all subjects who did not take a dose of Received OL Sirukumab during Part B.
- “Received at Least 1 Dose of OL Sirukumab during Part B” will include all subjects who took at least one dose of OL Sirukumab during Part B.

The Baseline for Part B will be the last measurement done up to and including the Week 52 visit date of Part A.

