Subjects unable to follow the prednisone taper due to disease flare, adrenal insufficiency, or safety reasons will cease the blinded prednisone treatment and will be offered treatment with an investigator-defined, open-label corticosteroid rescue regimen in combination with double-blind injections of sirukumab or placebo for the full 52 weeks, without a requirement to withdraw from the study. This study has been designed to allow subjects who are unable to follow the prednisone taper to continue in the study and follow the assessments at each visit as specified in the protocol.

When considering use of rescue prednisone, investigators should carefully assess whether the symptoms are related to an inflammatory GCA flare which would signify failure of tapering or is more likely due to non-inflammatory symptoms which could represent adrenal insufficiency or other co-morbidities.

All subjects who complete Part A of the study will be eligible to enter Part B. The 2 populations of subjects expected to enter into Part B are:

- Subjects in remission at the primary 52-week endpoint. These subjects will discontinue the blinded study drug treatment on entry into Part B and will be followed for maintenance of response. However, in the event of a disease flare, they will have the option to receive, at the discretion of the investigator, open-label sirukumab 100 mg SC q2w for a maximum of 52 weeks during the first 52 weeks of Part B.
- Subjects not in remission, at the primary 52-week endpoint, or subjects who have not been able to taper prednisone during Part A. Upon entry into Part B, these subjects will have the option to receive, at the discretion of the investigator, open-label sirukumab 100 mg SC q2w for a maximum of 52 weeks.

For subjects who newly flare at any time during the first 52 weeks of Part B and require a treatment change, open-label sirukumab 100 mg SC q2w can be initiated within the first 52 weeks of Part B. The duration of treatment will be at the discretion of the investigator but must not exceed 52 weeks.

Treatment with open-label sirukumab 100 mg SC q2w must complete by Week 104 (the end of the extension phase). Corticosteroid use or the initiation of methotrexate therapy alone or in addition to sirukumab treatment during Part B will be at the discretion of the investigator.

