11.4.2. Endpoints from Part A Reported during Part B

The following efficacy endpoints will be summarized and listed for Part B as for Part A using the by-line as specified in [Section 11](#), unless otherwise specified. The visit displayed in the outputs will be the re-mapped visit as specified in [Section 11.5](#).

- Cumulative prednisone dose over time:
Derivation will be the same as for Part A, as described in [Section 8.2.1](#). Only corticosteroid rescue therapies, as defined in [Section 3.3](#) and [Section 7.3](#) will be taken into account in the derivation of cumulative prednisone dose over time. All medication taken the day after the Week 52 visit of Part A will be considered in the analysis.
An additional summary will be displayed taking into account prednisone dose taken during both Part A and Part B.
- Number of disease flares per subject over time:

Derivation will be the same as for Part A, as described in [Section 8.2.4](#). All events occurring the day after the Week 52 visit of Part A will be considered in the analysis. The summary table will not use the Part B by-line.

An additional summary will be displayed taking into account all flares occurring during both Part A and Part B.

- Proportion of subjects requiring hospitalizations for disease flare and number of hospitalizations for disease flare over time:
Derivation will be the same as for Part A, as described in [Section 8.2.5](#). All events occurring the day after the Week 52 visit of Part A will be considered in the analysis. The summary table will not use the Part B by-line
- Patient-reported outcomes including SF-36v2 acute, EQ-5D (5L), FACIT-Fatigue, Pain NRS, Steroid Impact Questionnaire, HAQ-DI, PtGA and PhGA are exploratory endpoints in Part B and will only be listed

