11.5. Adverse Events

Since some subjects may not take any study drug during Part B, all AEs (not only TEAEs) will be summarized for Part B. An AE for Part B is defined as an AE starting from the Part A Week 52 visit date or the first SC IP of the Part B open-label treatment, whichever is earlier, to the end of study.

All adverse events summary table will be duplicated:

- The first table will use the byline: “Never Received OL Sirukumab during Part B” vs. “Received at Least 1 Dose of OL Sirukumab during Part B”
- The second table will use the following byline:
 - “Exposed” adverse events: Defined as all AEs occurring within 16 weeks after Sirukumab (SC IP or OL Sirukumab intake during Part B)
 - “Non-exposed” adverse events: Defined as all AEs not occurring within 16 weeks after Sirukumab (SC IP or OL Sirukumab intake during Part B)

It is important to note that all adverse events occurring during Part B within 16 weeks after the last intake of SC IP will be considered as “Exposed”, even if a subject never took OL Sirukumab during Part B.

No adverse events leading to discontinuation of study that is related to prednisone study drug will be displayed since prednisone study drug is only taken during Part A. TEAE related to prednisone will be displayed for Part B (instead of related to prednisone study drug for Part A).

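### SAP Section 11 groups Part B outputs by ever versus never taking open-label sirukumab, so delayed switchers' data from before their first open-label dose appear in the treated group

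*SAP*

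**What the plan says.** The opening text of SAP Section 11 repeats the Part A safety summaries for Part B and states: "Each output will be split using a by-line which will contain information on Part B". The by-line has two levels, defined per subject. The treated level "will include all subjects who took at least one dose of OL Sirukumab during Part B"; the other level holds those who took none. Neither refers to when the first open-label dose was given.

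Open-label drug can start late. SAP Section 3.3 (like protocol Section 4.2.2) allows it at Part B entry for subjects not in remission or unable to taper, and also "For subjects who newly flare at any time during the first 52 weeks of Part B and require a treatment change".

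The Part B clock starts before any such switch. SAP Section 11.5 says "An AE for Part B is defined as an AE starting from the Part A Week 52 visit date or the first SC IP" of open-label treatment, whichever is earlier. Section 11 adds: "The Baseline for Part B will be the last measurement done up to and including the Week 52 visit date of Part A".

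There are two departures from the by-line. In Section 11.4.2 the flare-count and flare-hospitalisation tables are exempt ("The summary table will not use the Part B by-line"), while cumulative prednisone keeps it. In Section 11.5, "All adverse events summary table will be duplicated": the second copy is split into exposed and non-exposed events, the latter "Defined as all AEs not occurring within 16 weeks after Sirukumab (SC IP or OL Sirukumab intake during Part B").

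**The concern.** A by-line fixed by a subject's later treatment assigns earlier observations to a group that could not be known when they were made. For a subject who enters Part B in remission and switches some months later, everything recorded in between is displayed as if it belonged to someone on open-label sirukumab. Because the switch follows a new flare needing a treatment change, the run-up to it can carry disease activity and rescue steroid that then sit in the treated group.

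One Part B objective is the long-term safety of sirukumab. A reader comparing the two levels would naturally take the treated one as a picture of what happens on the drug. For delayed switchers it mixes time before the drug with time on it. The fixed Week 52 baseline does the same to change-from-baseline and worst-post-baseline summaries.

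**Working it through.** The plan states no figure on this point, so the check is on which outputs are touched, then on simple arithmetic.

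**1. Who is affected.** Let s be the Part B week of the first open-label dose. Subjects starting at entry have s = 0 and no earlier Part B time. Only subjects with s between 0 and 52 are affected.

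**2. Which outputs are affected.** Until the switch these subjects follow protocol Table 3, which fixes what earlier data can exist.

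- Vital signs and GCA disease activity: every Table 3 visit. The corresponding SAP summaries (Sections 9.3 and 9.4) take the ever/never by-line, with no other split. A subject starting at Week 24 contributes Weeks 4, 8, 12, 16 and 24 to the treated group, if the Week 24 assessments precede dosing.
- Cumulative rescue-steroid dose: counted from the day after the Week 52 visit, by-line kept, no other split. This is an efficacy output. Section 11 says only demographic, baseline and safety displays are produced for Part B, while Section 11.4 plans efficacy outputs; the two need reconciling.
- Hematology, chemistry, lipids and HbA1c: nothing routine after Week 16, and at a flare visit only if the flare is on or before Week 16. CRP and ESR continue at every visit.
- C-SSRS: to Week 16, then only at a flare or early-withdrawal visit.
- AEs and AESIs: the first set of tables is affected; the second set uses the exposure split.
- Flare counts and flare hospitalisations: not affected.

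**3. What the second AE table separates.** Its 16-week window runs from any SC IP, including the last Part A injection. The last injection date is an assumption: Week 52 or Week 50. Weeks before the switch classed as non-exposed are max(0, s − 16) or max(0, s − 14) respectively.

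- s = 12: 0 or 0 weeks of 12.
- s = 24: 8 or 10 weeks of 24.
- s = 36: 20 or 22 weeks of 36.
- s = 52: 36 or 38 weeks of 52.

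The first 14 to 16 weeks of Part B therefore count as exposed with no open-label dose given, and the exposed level merges Part A carry-over with open-label treatment. It is also unclear whether carry-over applies in Arms D and E: the definition names sirukumab, but the explanatory sentence says SC IP, which includes placebo.

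**4. Share of follow-up before the switch.** With L the last Part B week, share = s/L. L is bounded by the calendar. The original protocol is dated 11 May 2015, and early-withdrawal visits were complete by 30 November 2017 (SAP Section 1.1). That is 934 days, and 934/7 = 133.4 weeks. Removing 52 weeks of Part A leaves at most about 81 weeks of Part B.

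- s = 24, L = 60: 24/60 = 40%.
- s = 40, L = 60: 40/60 = 67%.

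L = 60 means 112 weeks (784 days) from randomisation, so randomisation by about 8 October 2015. The documents do not show that anyone qualifies.

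**The case against.** The best defence is that the core of Part B safety is already handled. Every AE summary is produced a second time with an event-level, time-based split, and the flare tables drop the by-line. Routine laboratory tests stop at Week 16 before a switch, so few later drug-free values can be misplaced, and the shares in step 4 do not carry over to laboratory or C-SSRS data. The labels are literal, the Part A arms remain the columns, nothing is tested, and by-visit listings show original and mapped visits, so a switch can be traced.

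Much of this stands and sets the limits of the point. It does not reach vital signs, signs and symptoms, CRP and ESR, or rescue steroid, which have no alternative split. The second AE table does not separate before from on open-label drug.

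A pre-dose baseline is also only a partial cure. For most laboratory tests the last value before the first open-label dose may be from Week 16 or earlier. For Arms A to C that is still within about 16 weeks of Part A sirukumab.

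A reader might go further and infer that the flare prompting the switch always lands in the treated group. The documents do not support that. Flare counts and flare hospitalisations are not split. Under protocol Appendix 4 a flare of expected severity is not an AE. It reaches the AE and AESI tables only if it qualifies there, for example as a severe flare, though it can appear in the signs-and-symptoms table.

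**Conclusion.** The point holds for delayed switchers. Their data before open-label treatment are displayed in the treated group for vital signs, signs and symptoms, rescue-steroid dose, the laboratory and C-SSRS results that exist by then, and the first set of AE and AESI tables. The second AE set is a partial remedy.

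The overall size is unknown, because neither the number of delayed switchers nor their start weeks are given. The 40% and 67% shares are illustrations resting on assumed start and exit weeks. With summaries descriptive after termination, the consequence is a risk of misreading rather than a wrong inference. With few subjects, though, one misplaced event would be visible.

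Two stronger readings should be resisted. One is that half of a switcher's Part B time could be misplaced, from 52/104. Part B Week 104 needs 156 weeks from randomisation. The calendar allows about 133, or about 150 with the 16-week safety follow-up and its one-week allowance. The other is that the untreated group consists of subjects who did not flare, so that the two differ whatever the drug does. Protocol Section 4.2.2 makes open-label drug optional and allows corticosteroid or methotrexate alone. That group therefore also includes flarers managed without open-label drug, subjects not in remission at Week 52 who did not take it, and any whose first flare came after Part B Week 52.

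**What to change.** In SAP Sections 11 and 11.4.2, define the by-line by time relative to the first open-label dose: *before or without open-label sirukumab* versus *on or after first open-label dose*, with delayed switchers contributing to both. Apply it to vital signs, signs and symptoms, laboratory tests, C-SSRS, cumulative prednisone and the first set of AE and AESI tables. State how records dated on the day of the first open-label dose are assigned.

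For the on-or-after block, show change from the last value before the first open-label dose alongside change from Week 52, with a note that for laboratory tests this value may date from Week 16 or earlier. Keep the exposed/non-exposed AE tables, and say whether the 16-week carry-over applies after placebo.

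The cost is SAP wording and one derived period flag. Section 11.2 already uses the date of the first Part B injection, so no new data are needed. The downside is a few more tables, some with sparse cells.

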11.1. Analysis Set

11.1.1. Intent-to-Treat – Part B

The Intent-to-Treat – Part B (ITT – Part B) set will include all randomized subjects who received at least 1 dose of SC investigational product (IP) in Part A and entered Part B. In the event that there is a discrepancy, all subjects in the ITT – Part B set will be analyzed according to the treatment they were randomized to receive in Part A and not according to what they actually received in Part A. The ITT – Part B set will be used for the summaries of demographic, background, disposition and efficacy outputs in Part B.

11.1.2. Safety – Part B

The Safety – Part B set will include all randomized subjects who received at least 1 dose of SC IP in Part A and entered Part B. All subjects in the Safety – Part B set will be analyzed according to the treatment actually received in Part A and not according to the treatment they were randomized to receive in Part A, in the event there is a discrepancy. The Safety – Part B set will be used to analyze all of the safety endpoints in Part B.

11.2. Extent of Exposure

The following 3 parameters will be reported on the Safety set:

- Total number of injections a subject receives during Part B.

- Duration of SC IP treatment (weeks): defined as (Date of last SC IP dose in Part B – Date of first SC IP dose in Part B + 1 day) / 7. Only complete dates will be used when calculating duration of treatment. First and last injection dates will be used, regardless of any missed doses.
- Duration of SC IP exposure (weeks): defined as (Date of last SC IP dose in Part B – Date of first SC IP dose in Part B + 112 days) / 7. Only complete dates will be used when calculating duration of exposure. First and last injection dates will be used, regardless of any missed doses.
- Cumulative SC IP dose: defined as the total dose in mg a subject receives during Part B.

No compliance will be calculated for Part B.

11.3. Concomitant Medications

Concomitant medications for Part B are defined as those medications which are taken on or after the Part A Week 52 visit date or the first SC IP of Part B open-label treatment, whichever is earlier.

11.4. Efficacy Analysis

11.4.1. Endpoints Specific to Part B

The following endpoints are specific to Part B and will be displayed only on the subset of subjects in sustained remission at the Week 52 visit of Part A and enrolled in Part B:

- Proportion of subjects in sustained remission over time (including week 24):
Subjects who remained in sustained remission without requirement for rescue therapy or treatment change at each scheduled visit of Part B will be defined as subjects having achieved all of the following criteria:
Subjects in sustained remission at the Week 52 visit of Part A, as defined in [Section 8.1](#).

AND

Absence of disease flare:

Flare is determined by the investigator and defined as the recurrence of symptoms attributable to active GCA, with or without elevations in ESR and/or CRP.

The following rule will be used to assess absence of disease flare:

“Has the patient flared since their last visit?” should be answered “No” at each scheduled and unscheduled visit from any Part B visit up to Week X visit of Part B on the Clinical Assessment of GCA eCRF page.

AND

No requirement for rescue therapy at any time through Week X of Part B

If any concomitant corticosteroid medication when the unit is not in (Actuation, Application, Area under curve, Cubic centimeter, Cells, Cells per kilogram, Fingertip unit, Drops, Gum, Inhalation, Kilocalories, Minimum alveolar concentration, Mega becquerels (MBq), Millicurie, Nebule, Patch, Powder, Puff, Ring, Spray, Suppository) or any of concomitant non-corticosteroid medication identified as “GCA related” with the question “Was drug administered as a rescue medication?” ticked as “Yes” and if the first SC IP date \leq Concomitant medication start date \leq Week X visit date, then the subject will fail the criterion.

AND

No requirement for treatment change at any time through Week X of Part B

If any OL Sirukumab dose is taken prior or on the Week X visit of Part B, subject will fail the criterion.

If all of the 4 criteria are met, subject will achieve the endpoint at the Week 24 visit of Part B. If 1 of the 4 criteria is not met, the subject will be considered as not meeting the endpoint. For more details on imputation of missing data for the primary endpoint, please refer to [Section 4.6.2.1](#).

Given study termination, only the subset of subjects who attended the Week X visit of Part B or who discontinued study treatment or withdrew from study prior to the 10th of October 2017 will be included in this analysis.

The proportion of subjects achieving the endpoint over time will be presented by Part A treatment group. Subjects achieving the endpoint will be categorized by the criterion they failed to achieve. A listing will be produced with the detail of each criteria met or not met over time.

- Time to first disease flare for subjects in sustained remission at Baseline of Part B:

Only subjects who achieve sustained remission at the Week 52 visit of Part A will be included in this analysis.

Time to first disease flare after clinical remission is the time (days) from the Week 52 visit date to the earliest disease flare date:

Subjects without disease flare at the time of the analysis will be censored at the date of their last visit.

A Kaplan-Meier analysis will be summarized. The number of subject achieving clinical remission, as well as the number of subjects with a disease flare and the number of subjects censored with their censoring reasons will be summarized. 25th percentile, median and 75th percentile time to first flare will be summarized in days for each treatment group.

